5.3.5. Multiplicity of testing

Due to the exploratory nature of the sub-study, no adjustment for multiplicity of testing will be done. The level of the p-value will be used to assess the strength of the findings.

5.3.6. Properties of diagnostic tests Analysis

Considering successively the results of (1) TgSGP-PCR in skin (primary diagnostic parameter), and (2) IHC, TBR-PCR and/or 18S-PCR in skin (secondary diagnostic parameters), as validated diagnostic methods, the relative specificity, relative sensitivity, positive and relative negative predictive values of multiplex qPCRs, multiplex RT-qPCRs and SHERLOCK on skin, blood and DBS will be analyzed at enrolment. Four analyses will be performed for skin, blood, DBS and considering the result of any of the three samples.

Based on the placebo group data, the association between baseline and 4 months diagnosis results will be estimated through Cramer V coefficient for each diagnostic test and combination of diagnostic tests. The test or combination of tests providing the best association (reproducibility of baseline result) will be used for ranking tests. Other properties: relative sensitivity, relative specificity, predictive values, Cohen Kappa coefficient will also be used for ranking tests alone or in combination. Multicriteria ranking (sum of ranks) will be performed and the primary analysis will be redone on this new reference (best multicriteria rank) and each diagnostic test property will be computed with respect to this new reference.

6. Statistical software

All statistical analyses and generation of TLFs will be done using SAS software. Copyright © 2016 SAS Institute Inc¹¹.

7. Shell Tables, Listings and Figures (Attached separately)

8. References

- 1. International Conference on Harmonisation; Guidance on Statistical Principles for Clinical Trials *E9; Availability--FDA. Notice.* Vol 63.; 1998.
- 2. International Conference on Harmonisation: Structure and Content of Clinical Study Reports E3, Japan and USA.; 1995.
- 3. Investigator Brochure Acoziborole V4.0 12 November 2019.

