## 8.4. Exploratory assessments

For subjects participating in the TrypSkin exploratory sub-study, the following samples will be taken at screening (baseline) and 4 months (EoS):

- 3 mL fresh blood (in nucleic acid-preservative buffer) and 5 DBS
- Two 2 mm-skin-punch biopsies on the right back shoulder under local anaesthesia

Samples will be shipped to specialised partner laboratories (Institut National de Recherche Biomédicale [INRB], Institut Pasteur Guinea and Institut Pasteur Paris and Institute of Tropical Medicine [ITM] Antwerp) for the following analyses:

1- Molecular detection of trypanosomes:

- Common automatised extraction of total nucleic acids (TNAs) from fresh blood, DBS and skin biopsies
- On TNAs from fresh blood and skin (main validated diagnostic methods):
  - For all samples: TBR-PCR and 18S-PCR (*T. brucei s.l.*)
  - For TBR-PCR+ and/or 18S-PCR+ samples: T.b. gambiense-specific TgSGP-PCR
- On TNAs from fresh blood, DBS and skin (additional methods to be tested):
  - o qPCR detection using at least 2 targets
  - Multiplex RT-qPCR detection using novel targets
  - CRISPR-derived approach (SHERLOCK)
- 2- Immuno-histochemical detection of dermal trypanosomes:
  - At least 2 automatised IHC on Formalin-Fixed Paraffin-Embedded (FFPE) skin sections for all subjects with *T. brucei*-specific staining (Anti-Invariable Surface Glycoprotein 65 [ISG65] and Anti-cross reacting determinant [CRD] and secondary polymer amplification
  - Automatised acquisition and double *in silico* blind reading, pictures annotation and archiving
- 3- Preliminary tests for the detection of trypanosomes by Raman spectroscopy:
  - For each subject at each time point, one DBS from the field and one FFPE slide generated for IHC at IP Paris will be scanned by Raman spectroscopy at the University of Glasgow in the context of an exploratory procedure based on the measurements of biophysical parameters associated to the presence of trypanosomes.

• The results will not be uploaded in the central data base as the final analyses will rely on machine learning approaches after the end of the study.

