## Properties of diagnostic tests

Results of the following tests, alone or in combination, will be analysed in both groups at enrolment to assess the specificity, sensitivity, positive and negative predictive values of the new qPCRs, multiplex RT-qPCRs, and SHERLOCK in blood and/or skin:

- 1) TgSGP-PCR in skin (primary diagnostic parameter) and,
- 2) IHC in skin; TBR-PCR and 18S-PCR in blood and/or skin (secondary diagnostic parameters)

Results of all the new molecular tests, alone or in combination, will also be analysed in the placebo group at 4 months to test their repeatability.

Based on the placebo group data, the association between baseline and 4 months diagnosis results will be estimated through Cramer V coefficient for each diagnostic test and combination of diagnostic tests. The test or combination of tests providing the best association (reproducibility of baseline result) will be used for ranking tests. Other properties: sensitivity, specificity, predictive value, cost and rapidity for obtaining a response will also be used for ranking tests. Multicriteria ranking (sum of ranks) will be performed and the primary analysis will be redone on this new reference (best multicriteria rank) and each diagnostic test property will be computed with respect to this new reference.

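### SAP 5.3.6 restricts the TBR-PCR/18S-PCR reference to skin, so blood and DBS assays are scored only against skin results, although the protocol allows that reference in blood as well

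*SAP*

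**What the plan says.** **Protocol 10.8, Properties of diagnostic tests.** The new qPCR, RT-qPCR and SHERLOCK assays in blood and/or skin are assessed at enrolment against two references: "1) TgSGP-PCR in skin (primary diagnostic parameter) and", then "2) IHC in skin; TBR-PCR and 18S-PCR in blood and/or skin (secondary diagnostic parameters".

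**SAP 5.3.6.** The first reference is the same: "Considering successively the results of (1) TgSGP-PCR in skin (primary diagnostic parameter". The second becomes "2) IHC, TBR-PCR and/or 18S-PCR in skin (secondary diagnostic parameters), as validated diagnostic methods". The tests being assessed now cover three specimens: "multiplex qPCRs, multiplex RT-qPCRs and SHERLOCK on skin, blood and DBS will be analyzed at enrolment. Four analyses will be performed for skin, blood, DBS". The fourth analysis pools all three. No reason is given for taking blood out of the second reference.

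**Elsewhere in the SAP.** Section 1.2.2 defines the validated parameters (IHC, TBR-PCR, 18S-PCR) in skin, blood and DBS. Section 5.3.2 defines TBR-PCR and 18S-PCR as secondary parameters in the same three specimens. The objective in 1.2.1 compares methods in all three against gold-standard PCR and does not confine that PCR to skin.

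**Data available.** Protocol 8.4 runs TBR-PCR and 18S-PCR on every fresh-blood and skin sample, with TgSGP-PCR on the positives: "On TNAs from fresh blood and skin (main validated diagnostic methods". It lists none of these three PCRs on DBS.

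**Use.** In SAP 5.3.6 relative sensitivity, relative specificity, predictive values, kappa and placebo-arm repeatability enter a sum of ranks. The best-ranked test or combination becomes a new reference, on which the primary exploratory analysis is redone and all properties are recomputed.

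**The concern.** The specimens under test were widened while the reference was narrowed. A blood or DBS assay compared only with a skin punch can disagree with it for two reasons: the assay erred, or the parasites were in one compartment and not the other. The skin reference cannot tell these apart. A dermal-only carrier counts as a miss for every blood assay, and a blood-only carrier as a false positive.

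The objective is to compare detection methods in skin, blood and DBS. As written, the blood and DBS figures would partly describe how often blood and skin agree. They would also contribute to the choice of the new reference.

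**Working it through.** **1. The plan's own figure.** The documents state no sensitivity or specificity. The related planning figure is 690 evaluable subjects, for 20% prevalence and 3% precision. The usual formula gives n = z²p(1−p)/d² = 1.96² × 0.20 × 0.80 / 0.03² = 683, about 1% below 690, and 690 + 35 = 725 as stated. I use 690 and 20% only to size the illustration.

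**2. Inputs.**
- s, dermal prevalence: 20% (SAP 2.4.3, assumption 7).
- q = P(blood+ | skin+): not in the documents; assumed range 10-100%.
- r = P(blood+ | skin−): not in the documents; assumed range 0-10%.
- The assay is taken as perfect for parasites in blood, so any loss comes from the reference and not from the assay. Skin status is taken as correctly measured.

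**3. Formulas.**
- Skin reference: sensitivity = q; specificity = 1 − r; PPV = sq / [sq + (1−s)r].
- Composite reference (positive in blood or skin): sensitivity = [sq + (1−s)r] / [s + (1−s)r]; specificity and PPV = 100%.
- Error-free blood reference: sensitivity and specificity = 100%.

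**4. Results at s = 20%.**

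| q | r | Skin ref: sensitivity | Skin ref: specificity | Skin ref: PPV | Composite: sensitivity |
|---|---|---|---|---|---|
| 10% | 0% | 10% | 100% | 100% | 10% |
| 10% | 10% | 10% | 90% | 20% | 36% |
| 30% | 5% | 30% | 95% | 60% | 42% |
| 50% | 5% | 50% | 95% | 71% | 58% |
| 80% | 5% | 80% | 95% | 80% | 83% |
| 100% | 0% | 100% | 100% | 100% | 100% |
| 100% | 10% | 100% | 90% | 71% | 100% |

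The third row in full: sq = 0.20 × 0.30 = 0.06 and (1−s)r = 0.80 × 0.05 = 0.04. PPV = 0.06/0.10 = 60%, and composite sensitivity = 0.10/0.24 = 42%. Of 690 subjects, 138 are skin-positive, of whom about 41 are blood-positive; 552 are skin-negative, of whom about 28 are blood-positive.

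Prevalence does not change sensitivity or specificity against skin, but it does change PPV. With q = 30%, r = 5% and s = 5%, PPV = 0.015/(0.015 + 0.0475) = 24%.

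**5. If blood PCR is itself imperfect.** Stay with the third row, where 10% of subjects are blood-positive. Suppose blood PCR finds a share c of them and has no false positives. Scored against blood PCR, the perfect assay has sensitivity 100%, PPV = c and specificity = 1 − 0.10(1−c)/(1 − 0.10c). At an assumed c of 50%, PPV is 50% and specificity is 1 − 0.05/0.95 = 94.7%. At c of 30% and 90%, PPV is 30% and 90%, and specificity 92.8% and 98.9%. The sensitivity gain over the skin reference survives an imperfect blood PCR; the gain in specificity and PPV may not.

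**The case against.** **The protocol already scored across specimens.** Its first reference was TgSGP-PCR in skin only, applied to tests in blood and/or skin. This stands. A reader might infer that the SAP removed a same-sample comparison that the protocol had promised. The documents do not support that: only the blood part of the second reference has gone, and the protocol's blood and/or skin wording is not matched by specimen. Read as a composite, it would recover only part of the sensitivity.

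**Blood PCR is no gold standard.** Protocol 10.8 itself describes current specific molecular methods as having low sensitivity. This stands. One might set the skin-referenced figures against near-perfect same-sample figures, but that contrast assumes an error-free blood reference, which the documents do not support.

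**Non-specific is too strong.** One might also infer that good blood tests will look non-specific. That rests wholly on the blood-only share, for which no figure is given. Over the range assumed here, relative specificity stays at 90% or above, and with no blood-only carriers it is not affected.

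**Dermal carriage is a legitimate target.** The primary exploratory endpoint is dermal, the measures are labelled relative, and whether a blood test finds dermal carriers is worth asking. It follows that the ranking should not simply move to same-sample results. That could make a blood assay which misses dermal carriage the reference for a dermal efficacy question.

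**The ranking dilutes the effect.** Placebo-arm repeatability needs no skin reference, and all properties are recomputed against the new reference. This is partly right, but the skin-referenced scores still help choose that reference.

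None of this explains why 5.3.6 departs from protocol 10.8 and from SAP 1.2.2 and 5.3.2. Nor does 5.3.6 say that its four analyses use matched references.

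**Conclusion.** The point holds as an inconsistency between documents, and within the SAP, that has a real consequence. Followed as written, 5.3.6 caps the relative sensitivity of a blood or DBS assay at P(blood+ | skin+), apart from any false positives of the assay, and counts every blood-only carrier against it. For an assay perfect in blood, the assumed ranges give relative sensitivity of 10-100% and relative specificity of 90-100%. With full concordance and no blood-only carriers there is no loss.

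Some discordance is plausible. Participants are parasitology-negative in blood and/or lymph at entry, and the skin-positive subjects in the Guinea data were not confirmed by examination of blood and lymph. That evidence comes from parasitological examination, however, and says nothing quantitative about PCR. The main effect is on sensitivity; the effects on specificity and PPV are conditional on blood-only carriage.

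The sub-study is exploratory and unadjusted for multiplicity. The primary safety result is not touched. The correction is worth making because the blood data already exist.

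**What to change.** In SAP 5.3.6:

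1. Restore fresh-blood TBR-PCR/18S-PCR as a reference for the blood and DBS assays. Fresh blood is the nearest available reference for DBS, since protocol 8.4 lists no TBR-PCR or 18S-PCR on DBS. Leave the skin references for skin assays as they are.
2. For the any-sample analysis, define the reference as positive in skin or blood.
3. Keep the skin-referenced results for blood and DBS as a separate analysis, labelled 'detection of dermal carriage from blood'.
4. Keep the label 'relative' on all measures, including those against blood PCR.
5. State which results feed the sum of ranks, and keep the dermal target for choosing the reference on which the dermal efficacy analysis is redone.

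If the skin-only wording was deliberate, the SAP should say that dermal carriage is the sole target and justify the departure from protocol 10.8.

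The cost is SAP wording and further tabulation of results already planned. No new sample or assay is needed.
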